NB: See Summary of Product Characteristics for full details of contra-indications to LAIV. Note that **Fluenz is not recommended during pregnancy. Administration of another live vaccine (e.g. MMR) within the previous 4 weeks is no longer a contra-indication to LAIV administration, according to updated DoH guidelines.**

Children requiring oral steroids for their asthma management (ie. BTS Step 5) may be included in the study if they meet the following criteria:

1. Their asthma is stable on their current regimen and has been so for the previous 2 weeks
2. They are reviewed by the centre PI prior to inclusion in the study
3. Their Asthma Control Test score at inclusion is no lower than 20.

SUBJECT WITHDRAWAL

The primary outcome in this study involves a single visit to a hospital for administration of the intranasal vaccine. Subsequent withdrawal will affect only the assessment of delayed symptoms, a secondary outcome measure, which will be collected by telephone.

TRIAL CLOSURE

The study will be considered complete following enrolment of the last patient and completion of the study procedures in that patient, or at the end of the influenza season 2014-15. Upon review by the ISC, recruitment may be extended if target recruitment is achieved prior to end of the influenza season and additional funding is available.

[figure not shown]
The study will be placed on hold and, upon review of study data and discussion with the IDMC, may be terminated early if any of the following occur:

- One patient suffers an allergic reaction that warrants admission to the ICU and use of mechanical ventilation
- Death of a participant during the study period, from any cause
- Two similar SUSARs (Suspected Unexpected Serious Adverse Reactions) or the repetition of one SUSAR

A teleconference will be scheduled within 72 hours if any of the aforementioned situations occur. This conference will be attended by the members of the IDMC and the ISC. At this teleconference the clinical relevance of the findings will be determined and recommendations may be made by the IDMC which may include:

- requesting further information
- modifying the protocol
- stopping enrolment
- institute more frequent monitoring guidelines
- termination of study

STUDY VISITS, PROCEDURES SCHEDULE and Patient Flow Diagram

	Visit 1	Phone follow up at 72 hours	Follow-up (by phone or email) after 4 weeks
Written Informed Consent (parent/ guardian)	X		
Written assent (child)	X		
Medical assessment	X		

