Any allergic reaction happening during the observation period following vaccine administration will be managed according to local policy. For the purpose of this protocol, we would suggest that mild (non-anaphylactic) symptoms should be treated with a long-acting, non-sedating oral antihistamine such as cetirizine (at doses listed in cBNF). Symptoms of anaphylaxis will be treated according to UK Resuscitation Council guidelines (reproduced below).

ADVERSE EVENT REPORTING

DEFINITIONS

An **adverse event** is any occurrence or worsening of an undesirable or unintended sign, symptom, laboratory finding, or disease that occurs during participation, including occurrences that are not necessarily caused by or related to the administration of the medicinal product under investigation. An adverse event will be followed until it resolves or until 30 days after a participant terminates from the study, whichever comes first.

A **serious adverse event (SAE)** is defined as any adverse event that suggests a significant hazard. This includes but is not limited to any of the following:

1. Death: Any death that occurs during the study must be reported whether considered treatment related or not.
2. A life-threatening event: Any adverse therapy experience that, in the view of the investigator, places the participant at immediate risk of death from the reaction as it occurred.
3. Inpatient hospitalization or prolongation of existing hospitalization.
4. Persistent or significant disability.
5. An event that requires intervention to prevent permanent impairment or damage. An important medical event that may not result in death, be life threatening, or require hospitalization may be considered an SAE when, based on appropriate medical judgment, it may jeopardize the participant and may require medical or surgical intervention to prevent one of the outcomes listed above.

An **adverse reaction** is a AE attributable to the medicinal product under investigation, in this case the Fluenz vaccine. If the adverse reaction meets the above criteria (1-6) then it is termed a **Serious Adverse Reaction (SAR)**. Where the SAR is considered 'unexpected' i.e. its nature or severity is not consistent with the investigator's protocol, these events will be termed **serious unexpected severe adverse reactions (SUSARS)**.

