The adverse event or reaction can be described as 'expected' if it caused symptoms and/or signs that could be reasonably described as a consequence of an allergic reaction or following vaccination. Symptoms of an allergic reaction are defined as any described within this protocol, or those in the view of the investigator that are an expected consequence of vaccination.

Any symptoms requiring treatment for anaphylaxis (adrenaline, steroids, salbutamol) will be classified as a SERIOUS ADVERSE REACTION and must be documented on both the CRF as well as through completion of a SAE form. The local investigator should also make a notification to the MHRA should also be made through the yellow card scheme (<https://yellowcard.mhra.gov.uk/>).

For the purpose of this study, SARs and SAEs will only be collected where onset is within 72 hours of vaccine administration.

DOCUMENTATION OF ADVERSE EVENTS

Safety data will be recorded on a specifically designed case report form (CRF). All serious adverse events (SAEs) or reactions (SARs) will be reported on an SAE report in addition to CRFs. Safety data will be reviewed after three months by the Independent Data Monitoring Committee (IDMC). The IDMC has the authority to recommend termination of the trial because of safety findings.

Throughout the study, the investigator will record all adverse events on the appropriate CRF regardless of their severity or relation to study medication or study procedure. The investigator will treat participants experiencing adverse events appropriately and observe them at suitable intervals until their symptoms resolve or their status stabilizes. SAEs will be recorded on the SAE report form and reported to the ISC within 24 hours. SARs will also be reported to MHRA through the yellow card system.

GRADING AND ATTRIBUTION OF ADVERSE EVENTS

NON-ALLERGIC REACTIONS

The study site will grade the severity of adverse events experienced by study participants according to the criteria set forth in the NCI-CTCAE Version 3.0

(http://ctep.cancer.gov/protocolDevelopment/electronic_applications/docs/ctcae3.pdf).

This document provides a common language to describe levels of severity, to analyse and interpret data, and to articulate the clinical significance of all adverse events.

Adverse events will be graded on a scale from 1 to 5 according to the following standards in the NCI-CTCAE manual:

Grade 1 = mild adverse event.

Grade 2 = moderate adverse event.

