An interim analysis to assess the safety profile will be conducted after 100 participants have been recruited and received LAIV, the results of which will be reported to the IDMC Chair.

DATA MANAGEMENT

DATA COLLECTION

The following data will be collected:

- Patient demographics
- Current health to establish safety of immunisation
- Vaccination history:
 - previous exposure to influenza vaccine
 - previous reactions to vaccines
- Egg allergy:
 - Previous anaphylaxis? Tolerates baked egg? Respiratory symptoms to aerosolised egg?
 - Most severe reaction to egg: grading (WAO criteria)
 - Timing of most recent reaction
 - Recent diagnostic criteria: Skin test / serum specific IgE
 - Current egg avoidance
- Past medical history:
 - Medical indication for influenza vaccination or routine
 - Asthma: stable, uncontrolled
 - Active Allergic rhinitis
 - Current Medication including drug allergies
 - Other atopy: allergic rhinitis, eczema, other food allergies

Data will initially be submitted by a secure online data management system already used within Public Health England for vaccine surveillance. This data will be de-identified and accessible to the study team. Paper records kept locally at the study sites which will be identified by a study number.

DATA STORAGE

Paper records will be kept locally at the study sites which will be identified by a study number, within patient notes. De-identified patient data will be stored at the Immunisation Department, Public Health England and submitted to the study team using an online data management system.

De-identified study data will be kept for the statutory period and then disposed of securely. Local paperwork will be kept as part of the patient notes/CRF as per local policy.

ADMINISTRATIVE ASPECTS

ETHICAL COMPLIANCE

Approval will be sought from the West Midlands – Edgbaston National Research Ethics Committee. The study must be submitted for Site Specific Assessment (SSA) at each participating NHS Trust. The Study Coordination Centre will require a copy of the Trust R&D approval letter before accepting participants into the study. The study will be conducted in accordance with the recommendations for physicians involved in research on human subjects adopted by the 18th World Medical Assembly, Helsinki 1964 and later revisions

INFORMED CONSENT AND PARTICIPANT ASSENT

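### A second non-ventilated, non-fatal anaphylaxis case pauses the study automatically only if it is labelled unexpected; otherwise a pause is left to committee discretion

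*Protocol*

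**What the plan says.** All references are to the protocol.

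- **Trial Closure** lists three reasons to place the study on hold: "One patient suffers an allergic reaction that warrants admission to the ICU and use of mechanical ventilation"; a death from any cause; and "Two similar SUSARs (Suspected Unexpected Serious Adverse Reactions) or the repetition of one SUSAR". The joint meeting is tied to that list: "A teleconference will be scheduled within 72 hours if any of the aforementioned situations occur".
- **Adverse Event Reporting, Definitions** makes a serious reaction unexpected when its "nature or severity is not consistent with" the protocol. The same section lets a reaction be described as expected "if it caused symptoms and/or signs that could be reasonably described as a consequence of an allergic reaction or following vaccination", and adds: "Symptoms of an allergic reaction are defined as any described within this protocol".
- **The WAO grading table and Appendix 1** describe the signs of severe allergic reaction in full, including laryngeal oedema, respiratory failure, hypotension and the Brighton anaphylaxis criteria.
- **Definitions, and the section on grading allergic reactions,** class any symptoms needing anaphylaxis treatment as a serious adverse reaction (SAR). Serious Adverse Event Reporting has a separate sentence for SARs that are expected.
- **Other oversight.** SAE forms are due within 24 hours and are passed to the IDMC chair, the ISC chair and the sponsor. The IDMC reviews safety after three months and may recommend termination. Under Interim Analysis, "An interim analysis to assess the safety profile will be conducted after 100 participants have been recruited and received LAIV".

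**The concern.** Immediate allergic reaction is the primary outcome, and the study is meant to inform whether egg-allergic children can be vaccinated in primary care. Anaphylaxis is the serious form of that outcome. Yet the only hold criterion that works by repetition counts SUSARs, and the definitions point anaphylaxis towards the expected label.

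Two children who are treated with adrenaline and recover without ventilation could therefore meet none of the three criteria. Both chairs would know within about a day. Whether vaccination stops and the committees meet would then depend on how the investigator reads expectedness, or on the committees' own initiative.

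**Working it through.** **Step 1. Two anaphylaxis cases, neither ventilated nor fatal, against the hold list**

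| Criterion | Met? |
|---|---|
| ICU admission and ventilation | No |
| Death | No |
| Two similar or repeated SUSARs | Only if both are labelled unexpected |

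The label has two routes. On symptoms, the signs appear in the WAO table and Appendix 1, so the reaction can be called expected. On severity, an investigator could call it inconsistent with the protocol and hence unexpected. The text does not say which route prevails.

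**Step 2. Inputs**

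- n = 730 children, one dose each in the primary analysis. As context, the protocol's precision figure for 0/730 reproduces: 1 − 0.025^(1/730) = 0.504%, stated as 0.5%.
- General-use anaphylaxis rate from Background Information: 1 in 20,000 to 1 in 1,000,000 doses.
- Rates in egg-allergic children: not given. I assume 0.1% and 0.25% for illustration.
- Vaccination runs for five months. I assume even accrual and a review counted from the start of vaccination, so 730 × 3/5 = 438 children are vaccinated by month three and 730 − 438 = 292 remain.

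**Step 3. Chance of two or more cases**

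With independent cases, P(X ≥ 2) = 1 − (1 − p)^730 − 730p(1 − p)^729.

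- p = 1/1,000,000: about 0.00003%
- p = 1/20,000: 1 − 0.96416 − 0.03519 = 0.00065, or 0.065%
- p = 0.1%: 1 − 0.4817 − 0.3520 = 0.166, or 17%
- p = 0.25%: 1 − 0.1608 − 0.2943 = 0.545, or 54%

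**Step 4. When the second case falls, given that it occurs**

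Share after child m = 1 − P(X ≥ 2 in m) / P(X ≥ 2 in 730).

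| | 0.1% | 0.25% |
|---|---|---|
| After the 100-participant look | 1 − 0.0046/0.1662 = 97% | 1 − 0.0263/0.5449 = 95% |
| After the month-three review (child 438) | 1 − 0.0719/0.1662 = 57% | 1 − 0.2992/0.5449 = 45% |

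**Step 5. Children still to be vaccinated at the second case**

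The second case falls at child k with probability (k − 1)p²(1 − p)^(k−2), for k = 2 to 730. I average 730 − k over this distribution, first over all second cases and then over those with k > 438. Multiplying by p gives the further cases expected if nobody acted on the reports.

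| | 0.1% | 0.25% |
|---|---|---|
| All second cases: children remaining | 274 | 324 |
| All second cases: further cases | 0.27 | 0.81 |
| Second case after month three: children remaining | 140 | 151 |
| Second case after month three: further cases | 0.14 | 0.38 |

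**The case against.** **The oversight is real.** Every treated case produces an SAE form within 24 hours, which reaches both chairs and the sponsor, and the IDMC's power to recommend termination is not confined to the Trial Closure list. A reader might infer that repeated anaphylaxis could go unnoticed. The documents do not support that. What remains is the difference between prompt notice with discretion and a pause that happens by rule.

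**The expected label is not certain.** A reader might also infer that anaphylaxis must always be classed as expected, so the SUSAR criterion could never apply. That goes too far. The wording on expectedness is permissive, severity is a separate ground for calling a reaction unexpected, and Study Justification predicts few if any significant symptoms, so an investigator could reasonably call anaphylaxis unexpected. Read literally, the symptom list would even make a fatal reaction expected, because the WAO table includes death. The sound criticism is that the trigger hangs on an ambiguous label.

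**The event may be very rare.** At the only rates the protocol gives, two cases would hardly ever occur. The 17% and 54% come from assumed rates 20 and 50 times the top of that range. This stands as a limit on the size of the point. However, the documented range is for general use, and a hold rule is there for the case where prior expectation proves wrong.

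**The setting is favourable.** This is surveillance of a licensed vaccine, given in hospital with resuscitation facilities. Reserving automatic holds for the gravest events is a defensible choice. Parts of the study management pages were also not available to me, so a committee remit set out there cannot be excluded.

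**Conclusion.** The gap is in the text. The hold list counts repeated serious reactions only as SUSARs, and anaphylaxis without ventilation or death can be, and usually would be, labelled an expected SAR. The 24-hour reports, the 100-participant look and the three-month review do not require a pause or the joint teleconference.

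The practical size depends on an unknown rate. It is negligible at the general-use rate (0.065% or less) and material only if the true rate in egg-allergic children is nearer the assumed 0.1% or 0.25%. The timing figures also assume independent cases, even accrual and no action on the reports. The averages of 274 and 324 children cover all second cases, and a reader might take them as the number left after a missed month-three review. They cannot be that, since only 292 children remain at that point; the figures for that situation are 140 and 151.

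This is a cheap patient-safety improvement that should be made, not a flaw that undermines the study.

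**What to change.** Add one criterion to the Trial Closure list: *Two participants with anaphylaxis meeting the Appendix 1 definition, treated with adrenaline and assessed by the investigator as at least possibly related to LAIV, whether or not expected.*

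The hold should start on the second SAE report. The ISC and IDMC would confirm case status at the 72-hour teleconference, so the pause does not wait for committee judgement. Requiring adrenaline keeps out Appendix 1 cases that rest on minor symptoms and were not treated that way. The existing criteria, reporting route and scheduled reviews stay as they are.

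The cost is a possible short, reviewable pause within the five-month season, with the probabilities in step 3 as a guide to how often. There is also a small new task: someone must apply Appendix 1 to reported cases, since the protocol at present has the ISC classify allergic reactions by WAO criteria only.

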Sanofi Pasteur	Split virion BP	Inactivated	> 6 months	<50
MSD	Intanza	Inactivated	> 18 years	<24
Astra Zeneca	FLUENZ	Live attenuated	2 – 18 years	<240

Table 1: Ovalbumin content in influenza vaccines available in UK. Green book chapter 19: 207-209 (accessible at <http://immunisation.dh.gov.uk/category/the-green-book>)

A trivalent Live Attenuated Intranasal Vaccine (LAIV), given via the intranasal route, has been available in the United States for several years (8). It has demonstrated efficacy against influenza in children from 2-17 years old (9-12). LAIV is also grown in hens’ eggs and contains ovalbumin.

The safety of trivalent LAIV in non-egg-allergic children has been established predominantly in the MI-CP111 trial (13). Table 2 depicts the safety data collected during the first 10 days post vaccination. In this study, all children received both an intranasal spray and an intramuscular injection. The nasal placebo dose (saline) was associated with significant nasal symptoms (parent/subject reported) but on day 0-1 the incidence of this was considerably lower at only 12%. The quadrivalent vaccine has been found to have a similar safety profile [REF].

	Injection Site Reaction	Runny Nose/ Nasal Congestion	Fever >100°F	Fever >101°F	Fever >102°F
TIV n=4232	25%	46%	12%	7%	4%
LAIV n=4243	21%	57%	15%	8%	4%
	p <0.001	p <0.001	p <0.001	NS	NS

Table 2: Percentage of children with adverse events on days 0-10 after immunisation with LAIV from Study MI-CP111 (13)

LAIV is contraindicated in children under 2 years old. This is because there has been increased incidence of wheezing in children under 2 years old in the 4 weeks following immunisation (13, 14). This effect is not seen in older children (13, 15, 16), even in those with pre-existing asthma and wheeze (17). Post marketing surveillance data has not reproduced this signal (18). LAIV is not associated with new onset asthma (16).

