NUMBER OF SUBJECTS

- 730 children, on the basis of power calculations (see below).

EXPECTED DURATION OF STUDY

- Recruitment to commence 1st September 2014
- Clinical interventions to commence from mid-September 2014 for 5 months.

OUTCOME MEASURES

PRIMARY OUTCOMES:

- Immediate allergic reaction (occurring within 2 hours of administration)

SECONDARY OUTCOMES:

- Adverse events (of non-allergic aetiology) following administration
- Delayed onset allergic reaction (<72 hours following administration)
- Change in asthma control (by a validated questionnaire) pre and post LAIV

STUDY TREATMENT**DESCRIPTION**

Live Attenuated Intranasal Vaccine (Fluenz, Astra Zeneca), as provided for use by the Department of Health as part of the UK National Immunisation Schedule

At the current time, the Department of Health is planning to utilise the LAIV Quadrivalent vaccine (Fluenz Tetra, Astra Zeneca) for the influenza season 2014/15. However, in the event the quadrivalent LAIV is not available, vaccine supply will be with the trivalent LAIV.

DOSAGE AND ROUTE OF ADMINISTRATION

0.2 ml (administered as 0.1 ml per nostril). Immunisation must be carried out by nasal administration.

DOSE MODIFICATION

No dose modification proposed.

PREPARATION AND ADMINISTRATION OF STUDY DRUG

[figure not shown]
[figure not shown]
FLUENZ IS FOR NASAL USE only.

- DO NOT USE WITH A NEEDLE. Do not inject.

[figure not shown]

- FLUENZ is administered as a divided dose in both nostrils.
- After administering half of the dose in one nostril, administer the other half of the dose in the other nostril immediately or shortly thereafter.
- The patient can breathe normally while the vaccine is being administered – there is no need to actively inhale or sniff.
- Refer to the FLUENZ administration diagram (Figure 1) for step-by-step administration instructions.

[figure not shown]
Figure 1 FLUENZ Administration

[figure not shown]
1
Check expiry date
 Product must be used before date on applicator label.

[figure not shown]
2
Prepare the applicator
 Remove rubber tip protector. Do not remove dose-divider clip at the other end of the applicator.

[figure not shown]
3
Position the applicator
 With the patient in an upright position, place the tip just inside the nostril to ensure Fluenz is delivered into the nose.

4
Depress the plunger
 With a single motion, depress plunger as **rapidly as possible** until the dose-divider clip prevents you from going further.

5
Remove dose-divider clip

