 - E0 – avoids all foods containing egg in any form
 - E1 – tolerates egg in baked foods (cakes, biscuits) but not other forms
 - E2 – able to eat lightly cooked egg (e.g. scrambled egg, boiled egg) but reacts to raw egg in uncooked cake mixtures, fresh mayonnaise, ice cream etc.
3. Written informed consent from parent/guardian (or the patient themselves from age 16 years), with assent from children aged 8 years and above wherever possible.

EXCLUSION CRITERIA

1. **Clinical resolution of egg allergy**
2. **Contraindications to LAIV** (notwithstanding allergy to egg protein), which include:
 - a. Hypersensitivity to the active ingredients, gelatin or gentamicin (a possible trace residue)
 - b. Previous systemic allergic reaction to LAIV
 - c. Previous allergic reaction to an influenza vaccine (not LAIV) is a relative contra-indication, which must be discussed with the site PI to confirm patient suitability
 - d. Children/adolescents who are clinically immunodeficient due to conditions or immunosuppressive therapy such as: acute and chronic leukaemias; lymphoma; symptomatic HIV infection; cellular immune deficiencies; and high-dose corticosteroids*.

***High-dose steroids** is defined as a treatment course for at least one month, equivalent to a dose of prednisolone at 20mg or more per day (any age); or for children under 20kg, a dose of 1mg/kg/day or more.

NB: LAIV is not contraindicated for use in individuals with asymptomatic HIV infection; or individuals who are receiving topical/inhaled/low-dose oral systemic corticosteroids or those receiving corticosteroids as replacement therapy, e.g. for adrenal insufficiency.

- e. Children and adolescents younger than 18 years of age receiving salicylate therapy because of the association of Reye's syndrome with salicylates and wild-type influenza infection.

3. **Contraindication to vaccination on that occasion**, e.g. due to child being acutely unwell:

- a. Febrile $\geq 38.0^{\circ}\text{C}$ in last 72 hours
- b. Acute wheeze in last 72 hours requiring treatment beyond that normally prescribed for regular use by the child's treating healthcare professional
- c. Recent admission to hospital in last 2 weeks for acute asthma
- d. Current oral steroid for asthma exacerbation or course completed within last 2 weeks
- e. Recent use (within last 96 hours) of an antihistamine

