Existing data relating to skin prick testing to egg (where performed in routine clinical practice, according to BSACI guidelines (http://www.bsaci.org/Guidelines/Skin_Prick_Testing.pdf) and/or allergy blood tests (serum specific IgE to egg) will be collected from medical records, where available, to confirm sensitisation to egg.

No allergy testing will be performed as part of this protocol.

CLINICAL OBSERVATION / MONITORING OF PATIENTS BY CLINICAL STAFF

Patients will have baseline observations (temperature, heart rate, respiratory rate, oxygen saturations) performed prior to LAIV administration, with clinical respiratory and dermatological assessment at the same time.

Patients will be observed for at least 30 minutes after administration of LAIV, for symptoms of local or systemic allergic reaction. Symptoms (Total Nasal Symptom Score, TNSS) will be recorded at 10 and 30 minutes after vaccine administration, as follows:

Total nasal symptom score (TNSS)	
Rhinorrhoea	FOR EACH SYMPTOM, SCORE: 0 = no sign/symptom evident
Nasal congestion	1 = mild symptoms (sign/symptom clearly present, but minimal awareness; easily tolerated) 2 = moderate symptoms (definite awareness of sign/symptom that is bothersome but tolerable)
Nasal itch	3 = severe symptoms (sign/symptom that is hard to tolerate; causes interference with activities of daily living)
Sneezing	

[figure not shown]
US Department of Health and Human Services Food and Drug Administration, Allergic Rhinitis: Clinical Development Programs for Drug Products; 2000.
<http://www.fda.gov/downloads/Drugs/GuidanceComplianceRegulatoryInformation/Guidances/ucm071293.pdf>

Children will be observed in safe environment with appropriate clinical supervision and access to paediatric resuscitation facilities and trained staff, in the event of an anaphylactic reaction.

In the SNIFFLE study (2013/14 season), 8 children experienced possible local allergic symptoms following LAIV, all of which were mild and self-limiting. Symptoms commenced within 30 minutes of LAIV administration in all cases. Children will therefore be observed for 30 minutes, and if no symptoms are observed, discharged from the vaccine clinic. However, further clinical observations will be collected in the event of a clinical reaction, as per local policy.

TREATMENT OF ALLERGIC REACTIONS

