Allergic reactions to LAIV will be determined using the World Allergy Organisation (WAO) criteria for allergic reactions to immunotherapy, reproduced below. **For the purpose of this study**, mild symptoms of an allergic reaction (ie. non-anaphylactic symptoms) will be classified as non-serious adverse event, and should be documented on the CRF.

Any symptoms requiring treatment for anaphylaxis (adrenaline, steroids, salbutamol) **will be classified as a SERIOUS ADVERSE REACTION** and will be documented on both the CRF and a SAE form. The local investigator should also make a notification to the MHRA through the MHRA yellow card scheme.

On receipt of CRF / SAE forms, allergic reactions will be further classified by the ISC using World Allergy Organisation (WAO) criteria, which can be mapped to these grades and can be used to inform as to the appropriate NTI-CTCAE grade (Table 3).

Anaphylaxis will be defined as per the case definition and guidelines as described by the Brighton Collaboration Anaphylaxis Working Group (34) (see appendix 1).

WORLD ALLERGY ORGANISATION (WAO) GRADING SYSTEM FOR ALLERGIC REACTIONS TO IMMUNOTHERAPY

Grade 1	Grade 2	Grade 3	Grade 4	Grade 5

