
Symptom(s)/sign(s) of 1 organ system present*
 
Cutaneous Generalized pruritus, urticaria, flushing, or sensation of heat or warmth†
 
or
 
Angioedema (not laryngeal, tongue or uvular)
 
or
 
Upper respiratory Rhinitis - (eg, sneezing, rhinorrhea, nasal pruritus and/or nasal congestion)
 
or
 
Throat-clearing (itchy throat)
 
or
 
Cough perceived to originate in the upper airway, not the lung, larynx, or trachea
 
or
 
Conjunctival Erythema, pruritus or tearing
 
Other Nausea, metallic taste, or headache
	
Symptom(s)/sign(s) of more than 1 organ system present
 
or
 
Lower respiratory Asthma: cough, wheezing, shortness of breath (eg, less than 40% PEF or FEV₁ drop, responding to an inhaled bronchodilator)
 
or
 
Gastrointestinal Abdominal cramps, vomiting, or diarrhea
 
or
 
Other Uterine cramps
	
Lower respiratory Asthma (eg, 40% PEF or FEV₁ drop NOT responding to an inhaled bronchodilator)
 
or
 
Upper respiratory Laryngeal, uvula, or tongue edema with or without stridor
	
Lower or upper respiratory Respiratory failure with or without loss of consciousness
 
or
 
Cardiovascular Hypotension with or without loss of consciousness
	
Death

SERIOUS ADVERSE EVENT REPORTING

Serious adverse events and reactions must be reported to the PIs within 24 hours. An SAE/SUSAR form should be completed and faxed to the study coordination centre for all SAEs within 24 hours. This will then be communicated to the IDMC Chair, ISC chair and study sponsor. In the event of serious adverse reaction (expected), reporting should also include using the yellow card system.

In the case of suspected unexpected serious adverse reactions (SUSARS), the staff at the site should:

[figure not shown]
Complete the SAE case report form & send it immediately (within 24 hours, preferably by email or fax), signed and dated to the study coordination centre together with relevant treatment forms and anonymous copies of all relevant investigations.

Or

Contact the study coordination centre by phone and then send the completed SAE form to the study coordination centre within the following 24 hours as above.

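### No nasal symptom score is taken before dosing, so whether mild rhinitis counted in the primary outcome is new or pre-existing rests on unscored judgement

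*Protocol*

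**What the plan says.** All references are to the protocol; the SAP is not at hand.

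- **After dosing** (Clinical Observation / Monitoring of Patients by Clinical Staff): "Symptoms (Total Nasal Symptom Score, TNSS) will be recorded at 10 and 30 minutes after vaccine administration".
- **Before dosing** (same section): "Patients will have baseline observations (temperature, heart rate, respiratory rate, oxygen saturations) performed prior to LAIV administration, with clinical respiratory and dermatological assessment". No nasal score is listed.
- **Primary outcome** (Outcome Measures): "Immediate allergic reaction (occurring within 2 hours of administration"), with no minimum grade.
- **What counts as a reaction**: "Allergic reactions to LAIV will be determined using the World Allergy Organisation (WAO) criteria for allergic reactions to immunotherapy" (see the section Grading and Attribution of Adverse Events: Allergic Reaction).
- **WAO grade 1** includes "Rhinitis - (eg, sneezing, rhinorrhea, nasal pruritus and/or nasal congestion"). These are the four TNSS components.
- **Who arrives at the visit**: Exclusion Criteria list "Recent use (within last 96 hours) of an antihistamine". Active allergic rhinitis is a history item under Data Collection, not an exclusion.
- **Steps between a symptom and a reaction**: the adverse event definition requires something new or worsened, the investigator assigns causality, and the ISC then classifies allergic reactions by the WAO criteria.

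**The concern.** Egg-allergic children often have other atopic disease, and the protocol plans to record it. A child with active rhinitis who has taken no antihistamine for four days may have a runny or itchy nose before the spray is given. A non-zero TNSS at 10 or 30 minutes then has two readings, an unchanged nose or a reaction, and no scheduled measurement separates them.

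At stake are the incidence of any immediate allergic reaction, which is the primary outcome, and the comparisons of graded reactions. WAO grade 2 includes involvement of more than one organ system. Existing rhinitis plus one new sign elsewhere could therefore move a child from grade 1 to grade 2. An analysis plan can define a change score, but it cannot supply a pre-dose value that was never recorded.

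**Working it through.** **1. The plan's own precision figure.** Inputs are 0 events in 730 children (Sample Size Estimation), 0 in 433 doses, and 282 children in the previous study. The exact two-sided 95% upper limit for zero events is 1 − 0.025^(1/n).

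| n | Result | Stated |
|---|---|---|
| 730 | 0.504% | no more than 0.5% |
| 433 | 0.848% | <0.85% |
| 282 | 1.300% | <1.3% |

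All three reproduce. The 730 figure is conditional on no systemic or significant local reactions, and the note at the end of Appendix 1 classes local rhinitis as not systemic. Mild nasal symptoms do not enter this limit.

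**2. The route from a nasal symptom to the primary outcome.**

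| Step | What it needs | What is available |
|---|---|---|
| New or worsened (adverse event definition) | State of the nose before dosing | No pre-dose score; history of active rhinitis; general clinical assessment |
| Attributable to the vaccine (investigator) | Same | Same, by impression |
| ISC classification from the forms | Same | Scores scheduled only at 10 and 30 minutes |
| WAO grade | Symptom present | Isolated rhinitis suffices for grade 1 |
| Primary outcome | Allergic reaction within 2 hours | No severity threshold |

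The first three steps can stop existing rhinitis from being counted, but none has a scored baseline to work from.

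**3. Effect on the incidence.** Let a be the number of children whose existing rhinitis is counted as a reaction, and b the number whose true mild reaction is dismissed as existing rhinitis. Then:

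observed incidence = (true reactors + a − b) / 730

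One net child shifts the incidence by 1/730 = 0.137 percentage points. The sign of a − b is not known.

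**4. Whether the documents give a or b.** They do not. Two figures come near:

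- Study Justification reports 8 of 282 children (2.8%) with possible local allergic symptoms in the previous study. This counts suspected reactions, not false positives.
- Background Information says of nasal symptoms after saline placebo spray that "on day 0-1 the incidence of this was considerably lower at only 12" per cent. This is parent- or subject-reported over days 0–1, in children who also received an injection. It arises after a spray, so it is not a rate of pre-existing rhinitis.

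**5. Sensitivity under assumed rates.** The net over-count rates below are assumptions, applied as if there were no true reactors. The intervals are Clopper–Pearson.

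| Assumed net over-count | Children in 730 | 95% CI |
|---|---|---|
| 0.5% | 0.005 × 730 = 3.65, taken as 4 | 0.15–1.40% |
| 2% | 0.02 × 730 = 14.6, taken as 15 | 1.15–3.37% |

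Even a small net over-count would be visible in an incidence that is otherwise near zero. If dismissals outnumber over-counts, the shift is downward.

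**The case against.** **The protocol does not make every post-dose nasal symptom a reaction.** TNSS appears as monitoring and is absent from the outcome list and the analysis text. An adverse event must be new or worse, the causality categories weigh the child's clinical condition, and the ISC reviews. Non-allergic adverse events have their own secondary outcome. This stands. A reader might infer that existing rhinitis goes automatically into the primary incidence, and the text does not support that. What remains is that these safeguards rely on judgement without a score.

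**Current nasal disease is partly captured.** Active allergic rhinitis is listed separately from allergic rhinitis as other atopy, and there is a medical assessment at Visit 1. This also stands, but knowing that rhinitis is active does not show how it was graded just before the spray.

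**A baseline does not deal with spray irritation.** This is correct. Irritation begins after dosing and would be new or higher than pre-dose. Separating it needs attribution or a comparator.

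**The 2.8% and 12% figures do not measure the error.** Also correct. Applied to 730 they give 21 and 88 children (8/282 × 730 = 20.7; 0.12 × 730 = 87.6). It is tempting to read these as the inflation caused by the missing baseline, but neither is a rate of pre-existing rhinitis.

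**Subgroup distortion is speculative.** Asthma or recurrent wheeze is a planned subgroup and rhinitis is not. The documents give no evidence that misclassification would differ between groups.

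**The derivation rule could sit in the SAP.** The rule could, but the measurement has to be in the visit procedures.

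**Conclusion.** The point holds as a risk of misclassification in the mild nasal component of the primary outcome. No pre-dose TNSS is scheduled, isolated rhinitis qualifies as grade 1, and no severity threshold keeps it out. The error can run either way, and its size cannot be derived from the documents. A firm claim that the primary incidence is inflated would go beyond them.

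The 0.5% limit for systemic or significant local reactions stands as stated. The conclusion assumes that the case report form, which is not shown, holds no pre-dose nasal score beyond what the procedures list. It is a cheap improvement worth making, not a threat to the main safety statement.

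**What to change.** 1. In the monitoring section, add one TNSS immediately before dosing, with the baseline observations.
2. State that a nasal symptom counts towards the immediate-reaction outcome only if at least one TNSS component is new or higher than its pre-dose value.
3. Report the immediate reaction rate with and without isolated nasal symptoms. This is needed because the pre-dose score cannot separate non-specific effects of the spray; the second rate shows how far the result depends on them.

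The cost is one four-item score at a visit that already records it twice, about one extra minute per visit, and one CRF field. The sample size of 730 does not change.
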